5.5. Justification for Dose

The dose level proposed for the study of galcanezumab in cluster headache is 300 mg administered once monthly. Based on inhibition of capsaicin-induced dermal blood flow (CIDBF) and pharmacokinetic/pharmacodynamic (PK/PD) modeling of plasma CGRP concentrations (target engagement) from prior studies, it is presumed that this dose regimen will provide a high degree of pharmacological activity (greater than 90% effective in inhibiting CIDBF; about 90% decrease from baseline in unbound plasma CGRP concentrations), and be sufficient to test the effectiveness of galcanezumab for the treatment of cluster headache. A dose of 300 mg once monthly is predicted to replicate the exposure and have the same effect on CIDBF and unbound plasma CGRP as 150 mg every 2 weeks (Q2W), which yielded evidence of efficacy in migraine (Study ART-01). The safety and tolerability of galcanezumab supports dosing at 300 mg once monthly. Additionally, the parent trials, Study CGAL and Study CGAM, utilized galcanezumab 300 mg once monthly dosing.

6. Study Population

Patients diagnosed with episodic or chronic cluster headache that were enrolled in **and** completed one of the parent studies, Study CGAL or Study CGAM, are potentially eligible for this study.

If the sponsor or investigator identifies a patient who did not meet enrollment criteria for Study CGAR and was inadvertently enrolled, a discussion must occur between the sponsor clinical research physician (CRP) and the investigator to determine if the patient may be considered for Study CGAR. If both agree it is medically appropriate for the patient to be considered for Study CGAR, the decision must be documented by the investigator.

All patients must meet the following selection criteria. Eligibility of patients for study enrollment will be based on medical history, physical examination, clinical laboratory tests, ECG, and the inclusion and exclusion criteria described below.

Individuals who do not meet the criteria for participation in this study (screen failure) may be considered for rescreen once, for selected criteria, with approval from Eli Lilly and Company (hereafter Lilly) Medical (see below).

Prospective approval of protocol deviations to enrollment criteria, also known as protocol waivers or exemptions, are not permitted.

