6.1. Inclusion Criteria

1. Patients who **participated in and completed** either Study CGAL or Study CGAM. A study completer is defined as follows:
 - a. Study CGAL: a patient who has completed the double-blind treatment and post-treatment follow-up phases.
 - b. Study CGAM: a patient who has completed the double-blind treatment, open-label extension and post-treatment follow-up phases. However, if a patient entered Study CGAM prior to Study CGAR being open for enrollment, they will be considered a completer if they completed the double-blind treatment and post-treatment follow-up phases (e.g., opted not to participate in the open-label extension).
2. Investigator judges the patient as reliable to follow all study procedures, keep all study visits, and be compliant with study requirements.
3. Reproduction:
 - a. Women of child-bearing potential may participate in the study.
 - i. Women of child-bearing potential must test negative for pregnancy (based on a urine pregnancy test) at the time of enrollment and must agree to use either 1 highly effective method of contraception or a combination of 2 effective methods of contraception during the study. Women may choose to use a double barrier method of contraception. Barrier methods without concomitant use of a spermicide are not reliable or an acceptable method. Thus, each barrier method must include use of a spermicide. It should be noted that the

use of male and female condoms as a double barrier method is not considered acceptable due to the high failure rate when these methods are combined.

- b. Women not of child-bearing potential may participate in the study and include those who are:
 - i. Infertile due to surgical sterilization (at least 6 weeks after hysterectomy, bilateral oophorectomy or tubal ligation), congenital anomaly such as mullerian agenesis, or
 - ii. Post-menopausal, which is defined as:
 - a. A woman at least 50 years of age with an intact uterus, not on hormone therapy, who has had either
 - i. cessation of menses for at least 1 year, or
 - ii. at least 6 months of spontaneous amenorrhea with a follicle-stimulating hormone (FSH) level >40 mIU/mL; or
 - b. A woman 55 or older not on hormone therapy who has had at least 6 months of spontaneous amenorrhea; or
 - c. A woman at least 55 years of age with a diagnosis of menopause prior to starting hormone replacement therapy.
- c. Male patients agree to use at least 1 effective method of contraception during the study.

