9.1. Efficacy Assessments

The Patient Global Impression of Improvement (PGI-I) requests patients to mark the box that best describes your cluster headache condition since you started taking this medicine. The options in the displayed boxes are represented on a seven-point scale, with 1=very much better and 7=very much worse (Guy 1976).

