10.1. Sample Size Determination

The sample size for this study is not based on statistical or power considerations. This is an open-label safety study for patients who previously enrolled in and completed Study CGAL or Study CGAM. Therefore, the sample size is determined by the number of patients completing Studies CGAL and CGAM who choose to enroll in this study.

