10.3. Statistical Analyses

10.3.1. General Statistical Considerations

Statistical analysis of this study will be the responsibility of Lilly or its designee. Details of statistical analysis methods will be described in the statistical analysis plan (SAP) document.

Efficacy and safety analyses will be conducted on the evaluable analysis set. The evaluable analysis set includes all enrolled patients receiving at least 1 dose of the investigational product.

Baseline will be the time prior to receiving the first dose in this study. Additional baselines may be further outlined in the SAP along with details related to missing data.

Safety and efficacy analyses will be evaluated based on a 2-sided significance level of 0.05 unless otherwise stated. The 95% confidence intervals (CI) for the change from baseline will be presented. There will be no adjustments for multiplicity.

Any change to the data analysis methods described in the protocol will require an amendment ONLY if it changes a principal feature of the protocol. Any other change to the data analysis methods described in the protocol, and the justification for making the change, will be described in the SAP or clinical study report (CSR). Additional exploratory analyses of the data will be conducted as deemed appropriate.

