5.4. General Considerations

General aspects of statistical analyses are described below.

Unless otherwise specified, analyses will be conducted in the GMB-treated population, which includes all patients who are enrolled and receive at least 1 dose of study drug in Study CGAR, and analyses will be presented with 1 treatment arm. Safety analyses will be performed during the GMB-treated time and during the whole open-label treatment phase (SP II), which includes both GMB-treated time plus off-treatment time. GMB-treated time is composed of monthly dosing intervals, that is, the time from a GMB dose to the next monthly visit. The time between the first monthly visit that a dose is not administered and the dosing re-initiation visit is counted as off-treatment time. Baseline will be the time during SP I prior to receiving the first dose in this study. For safety analyses during the open-label treatment phase, any time after the first dose of GMB 300 mg will be considered as postbaseline period no matter if it is during an on-treatment or off-treatment month. For safety analyses during the GMB-treated time, only events that occurred during the GMB-treated time will be considered as postbaseline values.

Statistical analysis of this study will be the responsibility of Lilly or its designee. SAS[®] software will be used to perform most or all statistical analyses.

Any change to the data analysis methods described in the protocol will require an amendment ONLY if it changes a principal feature of the protocol. Any other change to the data analysis methods described in the protocol, and the justification for making the change, will be described in the SAP or clinical study report (CSR). Additional exploratory analyses of the data will be conducted as deemed appropriate.

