5.13. Efficacy Analyses

Descriptive summaries of the PGI-I, a 7-point scale, with 1=very much better and 7=very much worse (Guy 1976) will be presented at each time point collected during postbaseline, as described in the schedule of activities. It will be summarized as both a categorical and continuous variable.

The proportion of patients reporting a score of 1 ("very much better") or 2 ("much better") on the PGI-I 1 month after receiving their first dose will be reported.

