5.16.9.2. Immunogenicity Analyses to be Performed

To evaluate changes in immunogenicity data (ADA and NAb) after treatment, the number and percent of TE ADA evaluable patients who are TE ADA+ in Study CGAR will be tabulated.

The following analyses are planned:

- The incidence of TE ADA+ patients in CGAR postbaseline, by previous TE ADA status in the parent study (CGAL or CGAM) and at CGAR baseline. Because patients who enter Study CGAR will have differing levels of previous GMB exposure (0 to 15 months), this immunogenicity analysis will categorize patients in 3 groups, according to their previous GMB exposure in the parent study:
 - Study CGAL patients who received placebo (0 months of GMB treatment)
 - Study CGAL patients who received GMB (2 months of GMB treatment)
 - Study CGAM patients (12 or 15 months of GMB treatment)
- A listing of patients with TE ADA in CGAR postbaseline, including ADA and NAb results from both the parent study and CGAR.

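### The Month 1 PGI-I responder proportion is planned as one pooled figure across disease types and 0 to 15 months of prior galcanezumab, and the item's reference point is unclear for previously treated patients

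*SAP*

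**What the plan says.** **Endpoint.** SAP 4.3 and Protocol Table 4.1 name one endpoint for the effectiveness objective: the proportion with a PGI-I score of 1 or 2 one month after the first CGAR dose. SAP 5.13 repeats it. It also plans descriptive PGI-I summaries at every postbaseline collection, adding that "It will be summarized as both a categorical and continuous variable". Protocol 10.3.3 attaches an exact 95% CI to the proportion. SAP 5.13 names no interval.

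**Presentation.** SAP 5.4 states that "analyses will be presented with 1 treatment arm". SAP 5.5 and 5.7 expect no modelling with covariates, country or site. Nothing in 5.13 divides the PGI-I by disease type, prior exposure or state at entry.

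**Population.** Protocol Section 6 opens with "Patients diagnosed with episodic or chronic cluster headache that were enrolled in" and finished a parent study, CGAL or CGAM. Disease type and prior exposure are not among the baseline characteristics listed in Protocol 10.3.2.2 or SAP 5.10.

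**Prior exposure.** SAP 5.16.9.2 gives a range of 0 to 15 months and says "this immunogenicity analysis will categorize patients in 3 groups, according to their previous GMB exposure in the parent study". The groups are CGAL placebo (0 months), CGAL galcanezumab (2 months) and CGAM (12 or 15 months). Protocol 6.1, criterion 1b, says of patients who entered CGAM before CGAR opened that "they will be considered a completer if they completed the double-blind treatment and post-treatment follow-up phases"; for them the open-label extension is not required.

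**Reference point.** Under Protocol 9.1, patients choose the answer that "best describes your cluster headache condition since you started taking this medicine". The analysis baseline in SAP 5.4 falls in the screening phase, before the first CGAR dose.

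**The concern.** The plan treats prior exposure as important enough to group by for anti-drug antibodies, but gives no reason for not grouping the effectiveness endpoint the same way. Two difficulties follow.

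First, one proportion over unlike patients is a weighted average. Disease type and prior exposure are not on the listed baseline tables, so a reader of the planned outputs could not see the weights or judge whether response differed between the groups.

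Second, the PGI-I is a recalled change from a starting point, and patients may use different starting points. Two patients with the same course since CGAR Month 0 could score differently because one counts from the parent study.

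At stake is what the Month 1 proportion can be taken to mean for an episodic patient, a chronic patient, or a patient new to the drug.

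**Working it through.** **What can be reproduced.** Nothing numerical. Protocol 10.1 says "The sample size for this study is not based on statistical or power considerations", and neither document gives an N, an expected PGI-I rate, a precision target or stratum sizes. Protocol 10.3.1 sets a two-sided 0.05 level, but no PGI-I hypothesis is specified. Every rate, share and N below is therefore an assumption.

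**Step 1: effect of mix, two strata.** Pooled p = w × p1 + (1 − w) × p2, where w is the first stratum's share. The movement from w = 0.2 to w = 0.8 is 0.6 × (p1 − p2).

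| Assumed p1 / p2 | w = 0.2 | w = 0.8 | Movement |
|---|---|---|---|
| 50% / 50% | 50% | 50% | 0 points |
| 55% / 45% | 47% | 53% | 6 points |
| 60% / 40% | 44% | 56% | 12 points |
| 70% / 30% | 38% | 62% | 24 points |

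For the third row: 0.2 × 0.60 + 0.8 × 0.40 = 0.44, and 0.8 × 0.60 + 0.2 × 0.40 = 0.56.

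**Step 2: effect of mix, three exposure groups.** Assume rates of 60%, 50% and 35% for 0, 2 and 12 or 15 months. Shares of 20/20/60 give 0.12 + 0.10 + 0.21 = 43%. Shares of 40/40/20 give 0.24 + 0.20 + 0.07 = 51%.

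**Step 3: scale against sampling error.** At 50% response the exact (Clopper-Pearson) 95% CI is 39.8% to 60.2% for N = 100 and 42.9% to 57.1% for N = 200, half-widths of 10.2 and 7.1 points. In the 60/40 case, moving from an even mix to either extreme shifts the figure 6 points, a little less than those half-widths. In the 70/30 case it shifts 12 points, which is more.

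**Step 4: reference point.** Set Protocol 9.1 beside SAP 5.4. The item counts from starting the medicine; the baseline is before the first CGAR dose. No text tells a previously treated patient which start to use. Possible starts are parent-study treatment, the CGAM open-label extension and CGAR Month 0. Protocol 3.1 describes the parent studies as double-blind, so a placebo patient may also count from the parent study. If a share m of patients anchors there and this changes their response probability by d, the pooled figure shifts by m × d: 0.25 × 0.2 = 5 points, or 0.50 × 0.2 = 10 points.

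The same mismatch reaches SAP 5.14, which correlates EQ-5D-5L change from the CGAR baseline with Month 1 PGI-I.

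**Step 5: do the existing exposure groups cover everyone?** No. A CGAM completer admitted under criterion 1b without the extension cannot have the 12 or 15 months stated for CGAM. If that label means a 12-month extension with or without earlier active treatment, the difference of 15 − 12 = 3 months suggests 0 or about 3 months for such patients. That is an inference. The documents do not say how many such patients enrolled.

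**The case against.** The strongest reply is that the proportion validly describes the enrolled patients. There is one arm, one realised mix and no comparison to confound. The stated objective covers episodic and chronic patients together, no decision rule uses the figure, and both documents allow additional exploratory analyses. Strata would be imprecise: at 50% response the exact 95% CI is 27.2% to 72.8% for n = 20 and 33.8% to 66.2% for n = 40. All of this stands. It lowers the weight of the point but does not explain why a split made for antibodies is not made for effectiveness.

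Several stronger readings are tempting and are not supported:

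- That this is the sole effectiveness output. It is the only named endpoint; SAP 5.13 also plans PGI-I summaries at every postbaseline collection, though those are pooled too.
- That the SAP pools every other analysis. SAP 5.14 compares EQ-5D-5L change by active or remission status, and SAP 5.16 refers to integrated safety analyses with the parent studies in separate documents. For that reason no matching split of adverse events is requested here.
- That parent study can stand in for disease type. Neither document says which parent study enrolled which type.
- That episodic patients remit spontaneously within the first month. The protocol mentions remission but does not tie it to a type or a time course.
- That placebo patients surely count from CGAR Month 0. Blinding leaves this open.

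**Conclusion.** The point holds as a limit on interpretation. The Month 1 proportion is pooled over disease type and over a range of prior exposure that the SAP itself records, and its reference point may differ between patients.

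The size is unknown. Under the assumptions above, mix moves the pooled figure by 0 to 24 points, and by 12 points (44% to 56%) at rates of 60% and 40%. It moves only if response differs between strata, which the documents neither show nor exclude. The reference point could add 5 to 10 points under its own assumptions.

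A reader might conclude that the figure cannot be interpreted at all. That goes too far: it describes the treated population as a whole, but does not give a rate for either disease type or for patients new to the drug. The endpoint is tertiary and descriptive, and the primary safety conclusions do not depend on it.

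The exposure grouping in SAP 5.16.9.2 is a separate, firmer finding: its CGAM label does not fit every patient whom criterion 1b admits.

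**What to change.** 1. In SAP 5.13, keep the pooled Month 1 proportion. Beside it, report the proportion with n and exact 95% CI by diagnosed type (episodic, chronic) and by galcanezumab doses actually received in the parent study. Take type from the recorded diagnosis, not from the parent study. The interval also brings SAP 5.13 back into line with Protocol 10.3.3.
2. State in SAP 5.13 and the study report that the PGI-I reference point may precede the CGAR baseline for patients treated in a parent study, and possibly for blinded placebo patients, and interpret the pooled figure accordingly. The dose split will not fully separate these anchors, so the statement is needed as well.
3. In SAP 5.16.9.2, use the same actual-dose grouping, so that CGAM completers without the extension have a place. Fix the bands before the final lock.

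**Cost.** A few descriptive columns, assuming diagnosis and parent-study dosing records are available; the SAP already draws demographics and exposure from the parent trials. No new data collection is needed. The strata will be small: even at n = 80 and 50% response the exact interval is 38.6% to 61.4%. They should be labelled descriptive, with no test between them.

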5.14. Health Outcomes/Quality-of-Life Analyses

The European Quality of Life 5-Dimensions 5-Levels (EQ-5D-5L) questionnaire is a widely used, generic patient-rated scale that assesses current health status at the time of questionnaire completion, that is "today" (The EuroQol Group 1990; Herdman et al. 2011). The questionnaire consists of 2 parts. The first part assesses 5 dimensions (mobility, self-care, usual activities, pain/discomfort, and anxiety/depression) that have 5 possible levels of response (no problems, slight problems, moderate problems, severe problems, extreme problems). Answers to these 5 dimensions define a patient's health state. Given a patient's health state, the patient's country-specific health state index value can be obtained from the country-specific value set.

A country-specific value set is derived from valuation research that aims to measure how health is valued by people in a country. The valuation research includes a representative sample of participants from the general population in that country. In the valuation study participants are asked to value health by reviewing EQ-5D health states. The result from the valuation study is a value set for that country. The value set is essentially a set of weights to each of the levels in each EQ-5D dimension. A high weight means that people in that country believe that such a score has a high impact on health-related quality of life.

The health state index value is a single value on a scale from less than 0 (where zero is a health state equivalent to death; negative values are valued as worse than dead) to 1 (perfect health), with higher scores indicating better health utility. The UK population-based and US population-based health state index values are calculated based on the value sets from https://euroqol.org/wp-content/uploads/2018/02/EQ-5D-5L_Crosswalk_Value_Sets.xls

The second part of the questionnaire consists of a visual analog scale (VAS) on which the patient rates their perceived health state from 0 (the worst health you can imagine) to 100 (the best health you can imagine).

Descriptive statistics (n, mean, standard deviation [SD], range, median, 25th and 75th percentiles, min, max) for EQ-5D-5L Health State Index overall score based on US and UK population, scores for each of the 5 EQ-5D-5L dimensions (mobility, self-care, usual activities, pain/discomfort, and anxiety/depression), and EQ-5D-5L VAS current health score will be provided by visit. The number and percentage of patients with dichotomized responses (problems, no problems) for each of the 5 EQ-5D-5L dimensions will also be provided by visit.

To assess the correlation of EQ-5D-5L Health State Index Scores and VAS current health score with PGI-I and cluster headache status, the following analyses will also be performed:

- A correlation analysis between mean change from baseline in EQ-5D-5L with PGI-I at month 1, using Spearman's rank correlation coefficient.
- An Analysis of Variance (ANOVA) comparing mean change from baseline in EQ-5D-5L by cluster headache status (active or remission) at month 1 and month 6.

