Note: After V1, if V2 does not occur within 3 months of V1 (e.g., patient enters V1 in remission), prior to V2 an ECG, hematology, clinical chemistry, urinalysis, urine drug screen (UDS), HbA_{1C}, and serum pregnancy must be collected and eligibility confirmed prior to dosing at V2 (see footnote “d” in the SOA).

Study Phase II: SP II is the single-arm open-label treatment phase during which patients can receive galcanezumab 300 mg administered SC up to once a month. If a patient meets all eligibility requirements, a urine pregnancy screen will be conducted at the first dosing visit, prior to dosing to confirm that a female patient is not pregnant before administering investigational product. Following the first dose of galcanezumab, the patient should remain in the office for 30 minutes of observation. The site will have a scheduled telephone visit (V3) with the patient approximately 1 week after the first investigational product administration to collect spontaneously reported AEs.

Every month, the decision whether to administer a monthly dose will be based upon the study investigator’s judgment, which is not limited to, but includes assessment of the patient’s clinical symptoms and response as follows:

- Dosing is up to once monthly; more frequent dosing is not allowed. The full 300 mg dose is to be administered, changing the dose amount is not allowed.
- If the patient remits and dosing is halted, the patient may remain in the study, but they should have an office visit 1 month after the last dose to complete the procedures listed in

Event List F (Table 2.1). Dosing in this scenario may be reinitiated at the study investigator's discretion.

- Monthly telephone visits should be completed for patients who are not being dosed, but remain in the study (e.g., in remission).
- If dosing is temporarily interrupted due to a potential safety concern, dosing may be reinitiated at the study investigator's discretion following a discussion and agreement between the study investigator and Lilly Medical that re-initiation of dosing is appropriate.
 - At the office visit **prior to re-initiation of dosing** the following procedures: ECG, immunogenicity, pharmacokinetics (PK), hematology, clinical chemistry, HbA1c and urine pregnancy are to be collected. The urine pregnancy must be negative and the ECG should be evaluated for safety prior to dosing.

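### The EQ-5D-5L comparison by cluster headache status uses an ordinary ANOVA with no unequal-variance provision; naming Welch's version would protect its error rate at almost no cost

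*SAP*

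**What the plan says.** SAP 5.14 introduces two analyses with the words "To assess the correlation of EQ-5D-5L Health State Index Scores and VAS current health score with PGI-I and cluster headache status". The status analysis is "An Analysis of Variance (ANOVA) comparing mean change from baseline in EQ-5D-5L by cluster headache status (active or remission") at Months 1 and 6. The section names no Welch option, robust standard error, rank alternative or variance check, and SAP 5.5 anticipates no covariates. Read plainly, this is the ordinary one-way ANOVA with two levels.

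Both outcomes have a ceiling. The index runs "to 1 (perfect health), with higher scores indicating better health utility", and the VAS runs "from 0 (the worst health you can imagine) to 100 (the best health you can imagine").

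The number of patients is not set by statistical considerations (protocol 10.1, SAP 5.2), and neither document gives group sizes or SDs by status. Protocol 5.1 states "If the patient remits and dosing is halted, the patient may remain in the study". Such a patient has one office visit a month after the last dose (Event List F) and then monthly telephone visits (Event List G). In protocol Table 2.1, List F collects EQ-5D-5L and cluster headache status. List G collects only adverse events and serious adverse events.

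**The concern.** The pooled-variance test keeps its nominal level if the SD of change is the same in both groups, or if the groups are the same size. The design secures neither, because the groups are defined by how patients are doing after baseline and not by allocation.

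- **Size.** At Month 1, Table 2.1 collects both measures whether the patient is dosed (List C) or not (List F). At Month 6, List D applies to dosed patients. A patient undosed since before the previous month is on telephone visits and contributes nothing. Some remission patients therefore drop out of the Month 6 comparison, and unequal groups are likely there.
- **Spread.** If remission patients sit nearer the ceiling at both baseline and follow-up, their change scores will vary less than those of active patients.

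If both conditions hold, the pooled standard error is wrong for the difference. The test then either declares an association too often or misses a real one. This ANOVA is the only analysis specified for the tertiary endpoint that links EQ-5D-5L to cluster headache status.

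**Working it through.** The plan states no sample size, SD, power or p-value for this comparison, so there is no figure to reproduce. The group sizes, SDs and correlations below are assumptions. The 5% level is also an assumption here: protocol 10.3.1 says "Safety and efficacy analyses will be evaluated based on a 2-sided significance level of 0.05 unless otherwise stated", which does not name health-outcomes analyses.

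**1. Equivalence.** On a test data set, one-way ANOVA with two groups and the pooled t-test gave the same p-value (0.9545).

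**2. Formula.** Let A be active and R remission, with sizes nA and nR and SDs of change sA and sR.

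- Pooled variance: sp² = [(nA−1)sA² + (nR−1)sR²] / (nA+nR−2)
- Pooled SE = √[sp²(1/nA + 1/nR)]
- True SE = √(sA²/nA + sR²/nR)
- r = pooled SE / true SE
- Approximate real size of the nominal 5% test = 2[1 − Φ(1.96r)]

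**3. Worked case, 100 active and 25 in remission, SDs 0.25 and 0.10.** sp² = (99×0.0625 + 24×0.01)/123 = 0.05226. Pooled SE = √(0.05226×0.05) = 0.0511. True SE = √(0.000625 + 0.0004) = 0.0320. So r = 1.597 and the size is about 0.2%.

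**4. Same SDs, split reversed (25 active, 100 in remission).** sp² = (24×0.0625 + 99×0.01)/123 = 0.02024. Pooled SE = 0.0318. True SE = √(0.0025 + 0.0001) = 0.0510. So r = 0.624 and the size is about 22%.

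**5. Simulation with normal change scores and no true difference (20,000 data sets per case).** The first four rows are 80:20 splits. The last two have a total of 100 and an SD ratio of 1.5.

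| Active : remission | SD active, SD remission | ANOVA | Welch |
|---|---|---|---|
| 100 : 25 | 0.25, 0.10 | 0.2% | 5.2% |
| 25 : 100 | 0.25, 0.10 | 22.3% | 5.3% |
| 100 : 25 | 0.25, 0.15 | 0.9% | 5.0% |
| 25 : 100 | 0.25, 0.15 | 13.8% | 4.8% |
| 65 : 35 | smaller group has the smaller SD | 2.6% | 4.8% |
| 65 : 35 | smaller group has the larger SD | 8.0% | 4.9% |

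The SD ratios in the first four rows are 0.25/0.10 = 2.5 and 0.25/0.15 = 1.7.

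**6. When nothing goes wrong.** With 50:50 groups, ANOVA size was 4.8% to 5.2% for SD ratios from 0.5 to 2 (total 100). With equal SDs it was 4.9% to 5.0% for splits up to 90:10.

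**7. Role of the ceiling.** Three patterns were simulated with baseline and follow-up capped at 1.

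- Both groups equally near the cap: size 4.4% to 5.2% at every split.
- Remission nearer the cap at both times (SD of change 0.12 to 0.18, against about 0.22 in active): 0.7% to 2.4% with remission 20 of 100, and 8.9% to 16.1% with remission 80 of 100.
- Common baseline (mean 0.65, SD 0.20), with only the remission follow-up bunched near 1 (mean 0.95, SD 0.07, against 0.75 and 0.20 in active), at 100:25 and 25:100: 2.8% to 7.9%. Here change is roughly 1 minus baseline, so its SD stays close to the baseline SD.

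**8. Power.** For a true difference of 0.10 at 100:25 with SDs 0.25 and 0.10, ANOVA has about 49% and Welch 87%. With equal SDs of 0.20 at 100:25, ANOVA has about 60% and Welch 58%.

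**The case against.** The strongest reply is that the documents report none of the conditions for a serious distortion. They give no group sizes and no SDs by status, and the variable tested is change from baseline, not the capped score. Protocol 5.1 lets patients wait to enter screening until they are having or expect an attack. A widely spread in-bout baseline in both groups is therefore plausible, and then the size is only about 2.5% to 8%. This stands. Equal spread is not secured by the design, but neither is large inequality shown.

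Four stronger readings are tempting and are not supported:

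- **That the test is known to be too liberal at Month 6.** If remission is the group thinned by telephone visits and also has the smaller SD, the test is conservative (0.2% to 0.9% at 100:25). The 14% to 22% figures need remission to outnumber active by 4 to 1, and no split is stated.
- **That the ceiling by itself breaks the test.** It does not, as step 7 shows.
- **That the SAP's use of Spearman for PGI-I concedes the point.** PGI-I is a 7-point ordinal scale, which is reason enough for a rank correlation.
- **That planned confidence intervals for the status difference are wrong.** None is specified. Protocol 10.3.1 says "The 95% confidence intervals (CI) for the change from baseline will be presented", which is not an interval for a difference between status groups.

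Nor is a remission patient necessarily lost after one visit. Patients who resume dosing return to the dosing-visit schedule, and List F recurs after later halts. SAP 5.6 allows last observation carried forward when applicable, without saying whether that covers EQ-5D-5L or status.

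Finally, the comparison is tertiary, non-randomised and without a decision rule, and SAP 5.4 and 5.5 already allow exploratory and post hoc analyses. That limits the importance of the point but does not remove it.

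**Conclusion.** The point holds as a cheap improvement. The SAP specifies a test whose error rate depends on equal SDs or equal groups, in a comparison where the design secures neither. The distortion needs unequal sizes and unequal SDs of change together. It is mild (about 2.5% to 8%) for SD ratios up to about 1.5 at 65:35, or for ceiling bunching from a common baseline. It is large only near 80:20 with SD ratios of about 1.7 to 2.5: about 0.2% to 1% in one direction, 14% to 22% in the other. Welch's test stayed near 5% in every scenario. Every size and SD behind these figures is assumed, so they show sensitivity and do not predict this trial's result.

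One limit remains whichever test is used. Undosed remission patients on telephone visits give no Month 6 EQ-5D-5L, so that comparison covers a selected group.

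**What to change.** In SAP 5.14, replace the ANOVA with Welch's unequal-variance ANOVA, or keep the same linear model with HC3 standard errors, for the index and the VAS at Month 1 and Month 6. Report n, mean and SD of change by status, with a 95% CI for the difference from the same method.

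This is a change of one phrase plus a short reporting line, uses a standard software option and needs no new data. If the variances turn out equal, the loss is about 1 to 2 points of power. It does not recover the missing Month 6 data. The n by status will show how many patients the comparison rests on, and the text should say that undosed patients on telephone visits are absent from it.
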